BIOFEEDBACK VERSUS VAGINAL PALPATION TO TEACH A VOLUNTARY PELVIC FLOOR MUSCLE CONTRACTION TO WOMEN INCAPABLE OF PERFORMING IT. A NON-INFERIORITY RANDOMIZED CONTROLLED TRIAL

Brief summary:

Pelvic floor muscle training (PFMT) is the first line treatment of urinary incontinence (UI), anal incontinence (AI) and mild/moderate pelvic organ prolapse (POP) in women. However, 25 to 40% of women with pelvic floor dysfunction symptoms are unable to voluntarily contract their pelvic floor muscle (PFM) and PFM proprioception of this population is specially reduced. Literature is scarce about methods to facilitate a voluntary PFM contraction and improve PFM proprioception therefore, a specific protocol structured to teach PFM contraction is needed. The use of biofeedback could facilitate women's capacity to voluntary contract their PFM.

Study design:

Randomized, parallel (two arm), trial comparing biofeedback (experimental arm) versus vaginal palpation (active control, i.e. usual practice) to achieve a correct voluntary pelvic floor muscle contraction in women who cannot perform a correct contraction (i.e. grade 0, 1 or 2 on the Modified Oxford Scale). The trial hypothesis is that there is no difference between the two trial arms in the proportion of women achieving a correct voluntary contract (grade 3 or better).

Detailed description:

Arms of intervention: The study has two arms of interventions to which the patient will be randomly allocated to, both aiming is to provide an awareness/proprioception protocol with the purpose of enabling women to do a correct contraction: a proprioception protocol associated with vaginal palpation and feedback (CG) and the same protocol associated with biofeedback (BG). It will be a 12-weeks intervention delivered once a week during a 60-minute session by one of the two experienced physiotherapists who will provide the interventions in this study.

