- **WEEK 1: In clinics:** 30 minutes: educational component as previous discussed. 30 minutes: The studied protocol will be explained as well as the need to fulfill a diary with their home training routine that should be delivered to the evaluator at the 12-week assessment. At each session, the physiotherapist will oversee the diary, take notes about the frequency of training, and orientate if necessary. To promote a first contact with their PFM, it will be performed 1 set of PFM contraction associated with vaginal palpation or biofeedback of 6 fast contraction according to the randomized group. The resting time after each contraction will be five seconds. Possible doubts will be clarified. **At home:** All participants will be oriented to perform 3 sets of 6 fast contraction daily during the following week in the supine position. The resting time after each contraction will be five seconds and after each set will be 2 minutes.
- **WEEK 2-3: In clinics:** Training diary will be overseen, and possible doubts will be clarified. Training protocol will be different according to PFM function assessed on week 0. MOS 0: 3 sets of 6 fast contraction. The resting time after each contraction will be five seconds and after each set will be 2 minutes. MOS 1: 3 sets of 6 fast contraction and 3 sets of 6 contractions sustained for 3 seconds. The resting time after each contraction will be five seconds and 2 minutes after each set. **At home:** Training protocol will be different according to PFM function assessed on week 0. MOS 0: 3 sets of 6 fast contraction in supine position. The resting time after each contraction will be five seconds and after each set will be 2 minutes. MOS 1: 3 sets of 6 fast contraction and 3 sets of 6 contractions sustained for 3 seconds in supine. The resting time after each contraction will be five seconds and 2 minutes after each set.

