- **WEEK 4-6: In clinics:** Training diary will be overseen, and possible doubts will be clarified. Training protocol will be different according to PFM function assessed on week 3. MOS 0: 3 sets of 10 fast contraction. The resting time after each contraction will be five seconds and after each set will be 2 minutes. MOS 1: 3 sets of 10 fast contraction and 3 sets of 6 contractions sustained for 4 seconds. The resting time after each contraction will be six seconds and 2 minutes after each set. MOS > 2: 3 sets of 10 fast contraction and 3 sets of 10 contractions sustained for 6 seconds. The resting time after each contraction will be ten seconds and 3 minutes after each set. **At home:** Training protocol will be different according to PFM function assessed on week 3. MOS 0: 3 sets of 10 fast contraction, each set on a different position (i.e. supine, sitting and standing). The resting time after each contraction will be five seconds and after each set will be 2 minutes. MOS 1: 3 sets of 10 fast contraction and 3 sets of 6 contractions sustained for 4 seconds. Each set is supposed to be performed on a different position (i.e. supine, sitting and standing). The resting time after each contraction will be six seconds and 2 minutes after each set. MOS > 2: 3 sets of 10 fast contraction and 3 sets of 10 contractions sustained for 6 seconds. Each set is supposed to be performed on a different position (i.e. supine, sitting and standing). The resting time after each contraction will be ten seconds and 3 minutes after each set.
- **WEEK 7-9: In clinics:** Training diary will be overseen, and possible doubts will be clarified. Training protocol will be different according to PFM function assessed on week 6. MOS 0: 3 sets of 10 fast contraction and 3 sets of 5 contraction sustained for 3 seconds. The resting time after each contraction will be five seconds and after each set will be 2 minutes. MOS 1: 3 sets of 10 fast contraction and 3 sets of 6 contractions sustained for 4 seconds. The resting time after each contraction will be six seconds and 2 minutes after each set. MOS > 2: 3 sets of 10 fast contraction and 3 sets of 10 contractions sustained for 6 seconds. The resting time after each contraction will be ten seconds and 3 minutes after each set. **At home:** Training protocol will be different according to PFM function

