The two groups will receive a booklet and guidance to perform the training protocol at home on alternate days and a diary to register their adherence to the program. The guided protocol will be the same used during the supervised training on that specific week. Women will be oriented to choose the position to practice unsupervised sessions (i.e. supine, lateral, sitting and/or standing).

Outcome measures: The primary outcomes will be to gain the ability to perform a voluntary PFM contraction assessed by vaginal palpation and classified by the modified oxford scale (MOS). Women able to perform PFM contraction with both occlusion of the vaginal opening and inward movement will be considered able to perform a voluntary PFM contraction, this is the description of MOS grade 3.

Before the assessment, all participants will receive verbal instruction on PFM anatomy and function, as well as the correct way to perform its contraction. After verbal instruction, the participant will be placed in supine position with flexion of the hip, knee and feet supported on the stretcher. The physiotherapist will insert the index finger into the participant's vaginal canal after obtaining her consent and the participants will be instructed to perform three PFM contractions with the following verbal command: "squeeze my finger and pull as hard as you can get". PFM function will be classified according to the modified oxford scale, those with a rating ≥ 3 will be considered capable of performing a correct voluntary PFM contraction. The assessment will be performed in five timepoints: moment 0, after three, six, nine and 12 weeks of treatment. Participants will be assessed by the same trained physiotherapist in all five timepoints. It is expected to have two physiotherapists with more than 5 years with experience in women's health physiotherapy.

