Secondary outcomes will be presence of urinary incontinence (UI), UI severity and its impact on quality of life, self-perception of PFM contraction, adherence to supervised and unsupervised treatment, adverse effects, and satisfaction with treatment. Urinary symptoms will be assessed by the International Consultation on Incontinence Questionnaire-Short Form (ICIQ-UI-SF), absence of UI will be considered as a score of 0 in the ICIQ-UI-SF. Self-perception of PFM contraction will be a self-reported measure classified according to MOS. Adherence to supervised and unsupervised treatment will be assessed with physiotherapist registration of sessions and participants' exercise diary respectively. Adverse effects will be assessed using the following question "Did you experienced any discomfort or warm during supervised treatment?" at the last assessment timepoint. Satisfaction with treatment will be assessed using a numerical scale (0-10).

Eligibility: It will be included in this study: 1) Women aged 18 or over; 2) referred to the physiotherapeutic treatment of the Lucy Montoro Rehabilitation Center (Ribeirão Preto Medical School) or the Women's Health Reference Center (MATER) for any pelvic floor dysfunction; 3) unable to perform a PFM contraction (i.e. PFM function classified as 0 or 1 according to the modified oxford scale); 4) presence of urinary incontinence (i.e. ICIQ-UI-SF score ≥ 3) and; 4) agree to participate in the research by signing the informed consent form.

It will not be included in this study: 1) Women whose pelvic floor dysfunction has an associated neuropathy; 2) vaginal or urological symptoms of possible infections; 3) pelvic organs prolapse that makes it impossible to evaluate or conduct treatment (stage > 2 according to Baden-Walker Scale); 4) pregnant women; 5) women with cognitive impairment and; 6) women with intolerance or pain that prevents the conduct of research protocols.

Women who become pregnant while conducting the study will be excluded from the research.

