Randomization (sequence generation and allocation concealment): The randomization of the participants will be done using a computer-generated list of numbers (www.randomization.com). This list will be put in a sealed envelope and participants allocation will be concealed. The researcher responsible for assessment and inclusion of participants in the study will be blinded to which group participants will be allocated to. The research assistant who is responsible for generate the list of randomized numbers and seal the envelope as well as the research assistant responsible to perform patients' allocation will not be involved in the recruitment, assessment of participants or interventions.

Blinding of participants, and treatment providers: not possible

Blinding of outcome measurement: Primary outcome – blinded assessment by a physiotherapist not involved in delivery of therapy or with knowledge of group allocation. All other outcomes – not blinded because they are patient-reported.

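### Allocation is not stratified by baseline MOS grade, although the grade is known before randomisation and lies on the scale that defines success: a modest, avoidable loss of precision

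*Protocol*

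**What the plan says.** The section Randomization (sequence generation and allocation concealment) states: "The randomization of the participants will be done using a computer-generated list of numbers (www.randomization.com". It refers to that list in the singular: "This list will be put in a sealed envelope and participants allocation will be concealed". It mentions no stratification, blocking or minimisation, and it does not describe the list as simple or unrestricted. Study design gives two parallel arms; no allocation ratio is stated.

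Under Outcome measures, success on the primary endpoint is defined on the MOS: "those with a rating ≥ 3 will be considered capable of performing a correct voluntary PFM contraction". The same scale decides entry, but two places disagree on the grades admitted:

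- Eligibility: "unable to perform a PFM contraction (i.e. PFM function classified as 0 or 1 according to the modified oxford scale".
- Study design: "women who cannot perform a correct contraction (i.e. grade 0, 1 or 2 on the Modified Oxford Scale".

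Baseline grade also drives part of the programme. For weeks 2-3: "Training protocol will be different according to PFM function assessed on week 0". In those weeks grade 0 women do fast contractions only, and grade 1 women add sustained ones. From week 4 a re-assessed grade takes over, starting with: "Training protocol will be different according to PFM function assessed on week 3". At a given grade the training rule is the same in both arms.

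**The concern.** Few trials hold a baseline variable this close to their endpoint. A woman who enters at grade 0 has three grades to gain, and one at grade 1 has two. If grade 2 is admitted, as Study design says, some women have only one. If success differs by starting grade, which the distance to the cut-off makes likely, a chance excess of higher-grade women in one arm moves the observed difference in that arm's favour.

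The title declares a non-inferiority trial, so the result will turn on whether a confidence interval clears a margin. Avoidable noise in that interval costs power. A visible imbalance on the very scale that defines success would also invite dispute about the result, whichever way it falls. Restrictions on allocation have to be set before enrolment, so the protocol is the place for them; an analysis plan written later cannot supply them.

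**Working it through.** The protocol states no sample size, margin, success rate or grade mix, so there is no figure to reproduce. All numerical inputs below are assumptions.

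**Inputs.** Two baseline grades, 0 and 1 (Eligibility); 1:1 allocation (assumed); n women per arm; share q = 0.5 in the higher grade; success gap g between grades; no true difference between arms. Base case: n = 30 per arm, success 40% at the lower grade and 70% at the higher, so g = 0.30 and overall success is 55%.

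**Step 1: chance shift in the arm difference from grade imbalance.** SD = g × √(2q(1−q)/n) = 0.30 × √(2 × 0.25/30) = 0.30 × 0.1291 = 3.87 points. The 95% limit is 1.96 × 3.87 = ±7.6 points.

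**Step 2: how much of the total uncertainty that is.**

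- Unadjusted: overall p(1−p) = 0.55 × 0.45 = 0.2475. Half-width = 1.96 × √(2 × 0.2475/30) = 25.2 points.
- Stratified or adjusted: mean within-grade p(1−p) = (0.24 + 0.21)/2 = 0.225. Half-width = 1.96 × √(2 × 0.225/30) = 24.0 points.
- Variance ratio: 0.225/0.2475 = 0.909, a saving of about 9%. This equals about 10% more women (0.2475/0.225 = 1.10).

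The two steps agree: 7.6² + 24.0² = 57.8 + 576.0 = 633.8, and √633.8 = 25.2. The ±7.6 points is therefore already inside the ±25.2, not in addition to it.

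**Step 3: range.** 95% limit of the chance shift, in points, with q = 0.5. The variance saving takes overall success as 50%, so it is q(1−q)g²/0.25.

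| n per arm | gap 10 | gap 20 | gap 30 | gap 40 |
|---|---|---|---|---|
| 30 | 2.5 | 5.1 | 7.6 | 10.1 |
| 66 | 1.7 | 3.4 | 5.1 | 6.8 |
| 100 | 1.4 | 2.8 | 4.2 | 5.5 |
| 150 | 1.1 | 2.3 | 3.4 | 4.5 |
| Variance saved | 1% | 4% | 9% | 16% |

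The shift exceeds a few points only if the trial is small and the gap between grades is 20 to 30 points or more. A third baseline grade was not sized.

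**Step 4: is the test still valid without stratification?** An unadjusted one-sided non-inferiority test at 2.5% was simulated at the margin (100,000 runs; assumed margin 15 points, gap 30, q = 0.5). It rejected in 2.7%, 2.2% and 2.5% of runs at 30, 66 and 100 per arm. The mean estimated difference was −15.0 to −15.1 points against a true −15. There is no bias and no material inflation of type I error.

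**The case against.** The best case against the point is that omitting stratification is a legitimate choice. Randomisation is unbiased without it, the ordinary interval already carries the chance imbalance, and the gain in the base case is 1.2 points on a half-width of about 25. Adjusting for grade in the analysis would recover nearly all of that, and such adjustment is commonly placed in an SAP, which is not shown here. All of this stands, and it limits the point to a modest gain.

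Four stronger readings are tempting, and the document does not support them:

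- **That the design is biased, or that imbalance can manufacture or conceal a non-inferiority claim.** This is true only in the sense that any sampling error can, and the test controls that error (step 4).
- **That baseline grade fixes the whole programme.** It sets weeks 2-3 only. Later training follows re-assessed grades, and the rule is common to both arms, so it opens no separate route to imbalance.
- **That the list is known to be unrestricted.** The protocol is silent on this. Silence does not settle whether blocks are used, but blocks without strata would not balance grade anyway.
- **That grade is the strongest prognostic factor, or that the analysis ignores it.** The protocol does not rank prognostic factors, and the planned analysis cannot be seen.

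What the objection does not remove is that the variable is already collected, is measured on the outcome scale, and could be used in allocation at almost no cost.

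**Conclusion.** The point holds as a low-cost improvement, not as an error that undermines the trial. The protocol describes one list without strata, although each woman's distance to the success cut-off is known before she is allocated. The cost is precision and face validity. Under the base-case assumptions the half-width falls from about 25.2 to 24.0 points, a 9% saving in variance. With gaps of 10 to 20 points the saving is 1% to 4%. With a 10-point gap at 30 or more per arm, or a 20-point gap at 100 or more, the chance shift stays below 3 points. The direction does not depend on the inputs as long as success differs by grade; the size depends on them entirely.

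**What to change.** 1. Reconcile Study design and Eligibility on which baseline MOS grades are admitted. Strata cannot be defined until this is done.
2. Generate a separate list for each admitted grade, in permuted blocks of varying size, and say so in the randomisation section.
3. Estimate the week-12 difference in success stratified by or adjusted for baseline grade, with a Mantel-Haenszel risk difference or a standardised logistic model. This step is needed as well as step 2: an unadjusted interval would still be computed from the overall 0.2475 and would stay as wide.
4. If enrolment has begun, keep the existing list and pre-specify the grade-adjusted difference as the primary estimate, unless the SAP already does so.

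The cost is two or three short lists instead of one and a line of protocol text; no new data are collected. The one drawback is that the allocating assistant must be told the grade. The protocol already keeps that assistant out of recruitment, assessment and treatment, and varying block sizes help to protect concealment.
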